Table 14 - Analyses window definition for PK analyses - Stage 2	53
Table 15 - Operating characteristics of the study design assuming the dose 15 mg is selected for	
Table 16 - Operating characteristics of the study design assuming the dose 8 mg is selected for	
LIST OF FIGURES	
Figure 1 - Prespecified candidate of dose-response models	21
Figure 2 - Graphical illustration of the procedure for handling multiplicity	28
Figure 3 - Patient reported outcome (PRO) concents and questionnaires	38

VERSION HISTORY

This statistical analysis plan (SAP) for study EFC15392 is based on the protocol amendment 5 dated 17-July-2020. There are no major changes to the statistical analysis features in this SAP.

The first participant was randomized in the Stage 1 population on 11-Feb-2019. This SAP is approved before the futility analysis which is planned when all participants from Stage 1 have completed the first 9 months of treatment and approximately 30% have completed 18 months of treatment with Total Kidney Volume (TKV) available (or have prematurely discontinued).

Table 1 - Major changes in statistical analysis plan

SAP Version	Approval Date	Changes	Rationale
1	19-Jan-2021	The Population without trial impact (disruption) due to COVID-19 has been defined and additional analysis performed according to this population	In order to assess the impact of the COVID19 on the study
2	22-Jun-2021	Labels of treatment group updated from GZ/SAR402671 to venglustat	Clarification
		Added definition of baseline specific to Patient symptom diaries parameters and urine osmolality (see Section 4.1 and Section 4.8.3)	Clarification
		Update of the definition the treatment emergent period for patients who participate to the long-term extension LTS15823 (see Section 4.1)	Clarification
		Update of the tertiary endpoint related to TLV to be analyzed in participants with height adjusted total liver volume [htTLV] >1 L/m instead of > 2L/m (see Section 1.2 and Section 4.5.1)	Selection of participant with htTLV >2 L/m was to strict. According to HALT publication (1) it's acceptable to consider moderate PLD as htLV >1 L/m.
		Update of tertiary endpoint related to hospitalization to analyze rate and time of all-cause hospitalization (see Section 1.2, Section 4.5.1 and Section 4.8.5)	Clarification of endpoint
		PK populations and PK data analysis time windows have been updated (see Section 3 and Section 5.4)	Correction of time points as per protocol

22-Jun-2021	
Version number:	2

SAP Version	Approval Date	Changes	Rationale
		The two-step analysis is not applicable anymore and replaced by a single analysis of all data available on combined Stage 1 & Stage 2 analysis (see Section 1.1 and Section 4.9.3)	Following decision to discontinue EFC15392 and LTS15823 studies based on EFC15392 futility analysis
		Efficacy analyses on Stage 1 ITT population and combined Stage 1 and Stage2 population will be conducted on all data available up to database lock (see Section 4.1, Section 4.3.1). No multiple imputation will be done, only analysis on observed data will be performed (see Section 1.2.1, Section 4.3.1.1, Section 4.3.1.2, and Section 4.3.2.2).	
		As no post-baseline MRI data will be available in Stage 2 at the time of the study discontinuation, the analysis of TKV and TLV in Combined Stage 1 and Stage 2 will not be done (see Section 1.2.1, Section 4.4.2.2 & Section 4.5.2).	
		Secondary analysis of eGFR on all randomized participants will be replaced by descriptive summary across visit on the secondary Stage2 ITT population (see Section 3 and Section 4.3.2.4)	
		For all tertiary endpoints, due to the high number of missing data at month18 and month24, MMRM will be replaced by only descriptive summary by visits (see Section 4.5.2, Section 4.8.2, Section 4.8.3 and Section 4.8.4). For the secondary endpoints (BPI-Item3 & BFI Item3), in case the MMRM does not converge due to high number of missing data, then only descriptive summary by visits will be provided (see Section 4.4.1.2 and Section 4.4.2.2)	
		As no GM3 sample tested at the time of the study discontinuation, the analysis of GM3 will not be done (see Section 4.8.2)	
		Safety populations and all safety analyses on Stage 1 populations are removed. All safety analyses will be performed on the extended combined Stage 1 and Stage 2 safety population, including all participants with an eGFR between 30 and 89.9 mL/min/1.73 m ² at screening (see Section 3 and Section 4.7).	
		mGFR analysis has been removed as no data available (see Section 4.5.1).	

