1.2 OBJECTIVE AND ENDPOINTS

The objectives and endpoints as defined in the protocol are summarized in Table 2.

Table 2 - Objectives and endpoints

	Objectives	Endpoints
Stage 1		
Primary		
	 To determine the effect of venglustat on the rate of TKV growth in patients at risk of rapidly progressive ADPKD 	 Annualized rate of change in TKV based on magnetic resonance imaging (MRI) from baseline to 18 months
Secondary		
 Efficacy objectives 	 To determine the effect of venglustat on the rate of renal function (eGFR) decline 	 Annualized rate of change in eGFR (CKD-EPI equation) from baseline to 18 months
	 To determine the effect of venglustat on pain and fatigue, based on patient reported diary 	 Change in pain from baseline to 18 months, based on BPI Item 3 assessed from the daily symptom diary
		 Change in fatigue from baseline to 18 months, based on BFI Item 3 assessed from the daily symptom diary
	 To evaluate the PK of venglustat in ADPKD patients 	Plasma venglustat concentrations
 Safety/tolerability objectives 	 To characterize the safety profile of venglustat 	 Treatment emergent adverse events (TEAEs)/adverse events (AEs)/serious adverse events (SAEs), laboratory parameters, vital signs, electrocardiogram and findings from physical examination
	 To evaluate the effect of venglustat on mood using BDI-II 	 Change in score of BDI-II during the treatment emergent period
	 To evaluate the effect of venglustat on the lens by ophthalmological examination 	 Change in the lens clarity by ophthalmological examination during the treatment emergent period
Tertiary/exploratory		
	 To explore the impact of venglustat on total liver volume (TLV) (in participants with height adjusted total liver volume htTLV >1 L/m) 	 Annualized rate of change in TLV based on MRI (in participants with htTLV >1 L/m) from baseline to 18 months

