4.9.2 Interim futility analysis

An interim analysis for futility was performed when all participants from Stage 1 have completed the first 9 months of treatment and approximately 30% have completed 18 months of treatment with TKV available (or have prematurely discontinued).

The interim analysis was performed by the external independent statistician and was reviewed under the supervision of the DMC. The interim analysis primarily focused on the primary endpoint in Stage 1 (annualized rate of change in TKV) and stopping rules were based on this primary endpoint. Data monitoring committee also reviewed secondary efficacy endpoint (annualized rate of change in eGFR) and safety data (AEs, laboratory data, vital signs) available at the time of the interim analysis.

As per protocol, futility may be declared if the one-sided p-value of the primary endpoint at the interim analysis is >0.30. The one-sided p-value is determined from the Multiple Comparison Procedure described in Section 4.3.1.2. Based on simulations, it is expected that futility may be declared if the relative reduction versus placebo in TKV growth rate estimated at the interim analysis is approximately less than 15%. Probability to declare futility under different scenarios is presented in Section 5.6.1.

Of note, the futility rule is non-binding and provided as a guideline for the DMC but should not be considered as a strict stopping rule. In case the one-sided p-value observed at the interim analysis

is close to the pre-specified threshold, the DMC reviews the totality of data available at the time of interim analysis, including safety data (AEs, laboratory data, vital signs), and based on these data, may decide to overrule the futility rule.

If the DMC recommends continuing the study, then the Sponsor is informed of the recommendation and have no access to any unblinded results.

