If the DMC recommends stopping the study for futility, then unblinded results are made available to a limited number of Sponsor's senior management team. This limited team makes the final decision to stop or continue the study. To prevent internal exposure to unblinded interim data and informal or formal discussions that can present a substantial risk to the integrity of the trial and the Sponsor's ability to manage the trial without bias, only a small designated sub team of the Sponsor is unblinded, as described in DMC charter. This Sponsor's sub team is not involved in the direct conduct of the remainder of the study and any conduct of external committees related to the study to protect the overall integrity of the study.

In order to protect the global type one error in case the decision is taken to overrule the futility rule, non-binding futility rules are used for determination of alpha.

Based on the futility analysis reviewed by DMC on the 14 May 2021, the DMC recommended to stop the analysis for futility. The Sponsor's senior management team followed this recommendation and decided to discontinue the study.

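### Two Version History sentences, on approval timing and extent of change, do not hold for SAP version 2, which was approved 39 days after the DMC futility review

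*SAP*

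**What the plan says.** The SAP in force is version 2, approved 22-Jun-2021. Its Version History says of itself: "This SAP is approved before the futility analysis", an analysis it describes as still planned. The same page says: "There are no major changes to the statistical analysis features in this SAP". It names protocol amendment 5 as its basis.

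Section 4.9.2 treats the same futility analysis as finished: "An interim analysis for futility was performed when all participants from Stage 1 have completed the first 9 months of treatment". It continues: "Based on the futility analysis reviewed by DMC on the 14 May 2021, the DMC recommended to stop the analysis for futility". It then records that the sponsor's senior management accepted the recommendation and discontinued the study.

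Table 1 stands directly below the two Version History sentences and is titled as a list of major changes. It dates version 1 to 19-Jan-2021 and version 2 to 22-Jun-2021. From the two-step analysis onward, the rationale it gives is the discontinuation that followed the futility analysis.

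One version 2 change has a different rationale. The subset for total liver volume (TLV) moves from htTLV >2 L/m to >1 L/m because "Selection of participant with htTLV >2 L/m was to strict". Section 1.2 introduces the endpoint table with: "The objectives and endpoints as defined in the protocol are summarized in Table 2". Table 2 then prints >1 L/m. The protocol (amendment 07, 19 April 2021) keeps >2 L/m in Sections 5.1.3, 5.2.3 and 9.3.2.

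**The concern.** Readers go to the version history of a SAP to learn which rules were fixed before interim efficacy results existed. Here it gives one answer for the whole document, and that answer is right for version 1 and wrong for version 2. Someone relying on it would take the observed-data primary analysis, the pooled safety population and the >1 L/m liver subset as settled before the futility review.

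The liver-volume cut-off matters most in kind, though it is exploratory. It was not forced by missing data, it was approved after the review, and Table 2 presents it as the protocol's own definition. A subset redefined at that point should be recognizable as such in the report.

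**Working it through.** No power or alpha figure is in dispute. The check is a date comparison followed by a sorting of the changes.

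**Dates**
- Version 1, 19 January 2021, to the DMC review, 14 May 2021: 12 + 28 + 31 + 30 + 14 = 115 days before.
- DMC review, 14 May 2021, to version 2, 22 June 2021: 17 + 22 = 39 days after.
- Protocol amendment 07, 19 April 2021, to the DMC review: 11 + 14 = 25 days before.

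So the timing sentence is true of version 1 and false of version 2.

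**Signs that the paragraph was carried over.** It calls the futility analysis planned, whereas Section 4.9.2 reports it as done. It rests on amendment 5, although Table 9 of the SAP covers amendments 06 and 07. It dates amendment 5 to 17 July 2020, whereas the protocol's document history and SAP Table 9 both give 17 August 2020.

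**Whether the changes are major.** The sentence could mean relative to the protocol or relative to version 1. Neither reading fits version 2, for which Table 1 lists 14 rows. The substantive ones are:

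| Item | Protocol | SAP version 2 |
|---|---|---|
| Primary handling of missing data | Multiple imputation (11.4.2.1.1, Appendix J) | Observed data only (4.3.1.2, 4.3.2.2) |
| Sensitivity analyses | Observed data; control-based imputation | None (4.3.1.3, 4.3.2.3) |
| Final analysis | Two steps (11.5.3) | One analysis (1.1, 4.9.3) |
| Safety population | Stage 1; combined with screening eGFR 45 to 89.9; 30 to 44.9 separately (11.3.2) | One population, 30 to 89.9 (Section 3) |
| eGFR model including the 30 to 44.9 group; MMRM for other PROs | Modelled (11.4.2.4, 11.4.5) | Descriptive summaries (4.3.2.4, 4.5.2, 4.8.3) |
| TLV subset | htTLV >2 L/m | htTLV >1 L/m (1.2, 4.5.1) |

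Appendix 2 of the SAP, whose title promises changes to protocol-planned analyses, lists only protocol amendments. It records neither the dropped imputation nor the new liver-volume cut-off.

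**What did not change.** The mixed model, its Mayo-class weights and the contrast coefficients in Table 5 are the same in both documents. The multiplicity graph in SAP Section 4.6 (0.04 and 0.01, with weights 0.025 and 0.975) reproduces the levels in protocol Appendix J: 0.04 × 0.025 = 0.001, and 0.01 + 0.04 × 0.975 = 0.049.

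**Version 2 items that should not be called post-review.** The all-cause scope for hospitalization and the treatment-emergent period for extension patients come from amendment 07, which predates the review. The treatment-group labels are relabelling, and the PK time points are described as a correction to match the protocol.

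**The case against.** The strongest reply is that a reader can resolve the contradiction without leaving the section. Table 1 dates version 2 and cites the futility-based discontinuation, and Sections 1.1, 4.3 and 4.9.2 repeat it. That stands: nothing is hidden.

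It is also fair that many changes follow from stopping early. There was no post-baseline Stage 2 MRI, no tested GM3 sample and no mGFR data. The analysis that replaced multiple imputation was not invented afterwards, since the protocol already had it as a sensitivity analysis. Moving from models to descriptive summaries reduces inference. Safety analyses involve no testing, so the wider population touches no p-value. The liver-volume subset is exploratory and outside the multiplicity graph, and the combined-stage TLV analysis is not done at all.

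A reader might infer that version 2 was written with sight of the unblinded results. The documents do not support that. Section 4.9.2 confines unblinded results to a small senior team kept apart from the direct conduct of the remaining study, and it does not say who wrote version 2 or what they had seen. The authors knew that the study had stopped for futility, because Table 1 says so; more than that is not shown.

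These replies limit the size of the point, but they do not make the two sentences true of version 2 or Table 2 consistent with the protocol.

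**Conclusion.** The point holds as a documentation error that should be corrected. Two sentences in the Version History describe version 1 and are printed as a description of version 2; on timing the gap is 39 days on the wrong side of the review. Table 2 separately misdescribes one exploratory subset as the protocol's.

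Two larger conclusions are tempting and do not follow. One is that the final p-values have lost their pre-specified basis. The primary model, contrasts and alpha allocation are unchanged, and no effect on a confirmatory result is shown. The other is that every version 2 change is post hoc, when several trace to amendment 07 or are relabelling and corrections.

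The conclusion rests on the dates printed in the SAP and on Table 1 being a full account of what changed between versions. The text of version 1 is not among the documents, so for any single item the sponsor must confirm when it first appeared.

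**What to change.** 1. In the Version History, limit both sentences to version 1. Add that version 2 was approved after the 14 May 2021 DMC review, and state whether its authors were blinded to the comparative results. Correct the protocol amendment and date cited as its basis.
2. In Table 1 or Appendix 2, flag as post-review only the changes first introduced after that review: observed-data analysis as primary, removal of the remaining sensitivity analysis, the single final analysis, the redefined safety population, the models replaced by summaries, and the htTLV cut-off. Leave out items from amendment 07, relabelling and PK time-point corrections.
3. In Section 1.2 and Table 2, say that htTLV >1 L/m departs from the protocol's >2 L/m.
4. Report the Stage 1 TLV result for the >2 L/m subset beside the >1 L/m subset, in the same form.

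The cost is a few lines of wording and one exploratory table. The >2 L/m subset may hold few patients, so that table may be imprecise; its use is to show whether the change of cut-off altered the picture.

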## 9.3 EXPLORATORY ENDPOINTS

### 9.3.1 Stage 2 only

- Annualized rate of change in mGFR from baseline to 24 months (substudy).
- Annualized rate of change in eGFR (CKD-EPI equation) from baseline to 24 months in patients with a screening eGFR between 30 and 44.9 mL/min/1.73 m^2.

### 9.3.2 Stages 1 and 2

- Annualized rate of change in total liver volume based on MRI (in patients with htTLV >2 L/m) from baseline to 18 months, Change in:
  - Systolic BP during the treatment-emergent period,
  - Diastolic BP during the treatment-emergent period,
  - Pain (BPI), fatigue (BFI), and health status (EQ-5D-5L) from baseline to 18 months in Stage 1 and 24 months in Stage 2,
  - Nocturia from baseline to 18 months in Stage 1 and 24 months in Stage 2, based on patient reported diary,
  - Urine osmolality from baseline to 18 months in Stage 1 and 24 months in Stage 2 (in patients not on diuretic),
  - Type, frequency, and dosage of analgesic/OTC pain medication administration from baseline to 18 months in Stage 1 and 24 months in Stage 2,
  - Biomarkers associated with ADPKD (eg, FGF23 and ADMA) from baseline to 18 months in Stage 1 and 24 months in Stage 2,
  - Glucosylceramide (GL-1) and GM3 from baseline to 18 months in Stage 1 and 24 months in Stage 2.
- Rate of all-cause hospitalization.
- Time to confirmed 30% reduction in eGFR.

- Time to confirmed 40% reduction in eGFR.

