4.5 TERTIARY/EXPLORATORY ENDPOINT(S) ANALYSIS

4.5.1 Definition of endpoint(s)

In Stage 1 and Stage 2, the following endpoints are defined as exploratory efficacy endpoints:

- Annualized rate of change in TLV based on MRI from baseline to 18 months on participants with htTLV >1 L/m
- Change in:
 - Urine osmolality from baseline to 18 months in Stage 1 and 24 months in combined Stage 1 and Stage 2 (in participants not on diuretic at baseline)
 - Nocturia from baseline to 18 months in Stage 1 and 24 months in combined Stage 1 and Stage 2, based on the daily symptom diary (see Section 4.8.3)
 - Systolic BP during the treatment emergent period (see Section 4.7.3.1)
 - Diastolic BP during the treatment emergent period (see Section 4.7.3.1)
 - Biomarkers associated with ADPKD (eg, FGF23 and ADMA) from baseline to 18 months from baseline to 18 months in Stage 1 and 24 months in combined Stage 1 and Stage 2 (see Section 4.8.4)
 - Pain (BPI), fatigue (BFI) and health status (EQ-5D-5L) from baseline to 18 months in Stage 1 and 24 months in combined Stage 1 and Stage 2 (see Section 4.8.3)
 - Glucosylceramide (GL1) and GM3 from baseline to 18 months in Stage 1 and 24 months in combined Stage 1 and Stage 2 (see Section 4.8.2)
- Type, frequency, and dosage of analgesic/over the counter (OTC) pain medication administration from baseline to 24 months (see Section 4.8.3)
- Rate of all-cause hospitalization (see Section 4.8.5)

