4.5.2 Main analytical approach

As no post-baseline MRI data will be available in Stage 2 at the time of the study discontinuation the analysis of TLV in Combined Stage 1 and Stage 2 ITT population will not be done.

For other quantitative exploratory endpoints only descriptive summaries by visits will be provided.

The urine osmolality will be analyzed using the average of the 3 separate measurements performed between visit date - 3 and visit date + 1 at each planned visit performed within analysis time windows (see Table 12):

- first spot at visit day-2 am
- second spot the day of visit am
- third spot from the 24-hour urine sample, if any, else sample at the time of visit

All participants on oral diuretic medications at the time of the 1st IMP administration (ie, start date of medication prior to the 1st administration of IMP and end of medication after the 1st administration of IMP or missing) will be excluded from the urine osmolality analysis.

Analyses of pain medications and hospitalization will be defined in Section 4.8.3 and Section 4.8.5.

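### SAP version 2 keeps the Stage 1 liver-volume growth rate as an exploratory endpoint but names no method to estimate it, and Table 2 presents its changed population (htTLV >1 instead of >2 L/m) as protocol-defined

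*SAP*

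**What the plan says.** **The endpoint.** Protocol Section 9.3.2 defines it as "Annualized rate of change in total liver volume based on MRI (in patients with htTLV >2 L/m) from baseline to 18 months". SAP Section 4.5.1 keeps the rate with a different population: "Annualized rate of change in TLV based on MRI from baseline to 18 months on participants with htTLV >1 L/m". The Stage 1 part of SAP Table 2 has the same threshold: "Annualized rate of change in TLV based on MRI (in participants with htTLV >1 L/m) from baseline to 18 months". Section 1.2 introduces that table with "The objectives and endpoints as defined in the protocol are summarized in Table 2".

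**The population change.** SAP Table 1 logs it under version 2: TLV is to be analyzed in "participants with height adjusted total liver volume [htTLV] >1 L/m instead of > 2L/m". The rationale is "Selection of participant with htTLV >2 L/m was to strict", followed by a reference to a publication.

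**The analysis.**
- Table 1, version 2: "For all tertiary endpoints, due to the high number of missing data at month18 and month24, MMRM will be replaced by only descriptive summary". The row goes on to specify summaries by visit and points to Section 4.5.2, among others. A separate row cancels the TKV and TLV analyses in combined Stage 1 and Stage 2, because Stage 2 will have no post-baseline MRI.
- Section 4.5.2 repeats that cancellation for TLV, then says: "For other quantitative exploratory endpoints only descriptive summaries by visits will be provided".
- Section 5.4 places TLV, with TKV and several others, among endpoints whose time-point summaries use the planned visits. It also has a general rule that annualized-rate efficacy analyses use scheduled and unscheduled assessments.
- Section 4.3.1.2 writes out a linear mixed model for log10(TKV), and Section 4.3.2.2 extends it to eGFR. No section extends it to TLV.

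**The concern.** An annualized rate needs an estimator. The SAP names the rate and the population, but a programmer working from it would not know whether to fit a slope, tabulate TLV by visit, or do both.

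The reason given for going descriptive is missing Month 18 and Month 24 data. That is a reason to doubt an MMRM that targets the mean at a late visit. A random-slope model uses whatever scans each participant has, and the SAP keeps one for TKV on that basis.

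The threshold matters for a different reason. Someone who reads Section 1.2 without Table 1 would take >1 L/m as the protocol's population, and would have no >2 L/m result to set beside it.

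**Working it through.** This is mainly a comparison of text. The only arithmetic is two date intervals and one illustration.

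**1. Is a TLV rate model stated anywhere?** SAP 4.3.1.2 covers log10(TKV) and 4.3.2.2 covers eGFR. SAP 4.5.2 gives no model for Stage 1 TLV. SAP 5.4 says which readings and assessments enter an analysis, not how a rate is estimated. Protocol Section 11.4 gives no TLV model either.

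**2. Do Table 1 and Section 4.5.2 agree?** Table 1 covers every tertiary endpoint, and TLV is one. Section 4.5.2 deals with TLV first, dropping only the combined-stage analysis, then limits the descriptive rule to the others. Two readings follow:
- Table 1 governs: Stage 1 TLV is tabulated by visit and no rate is produced.
- Section 4.5.2 governs: a Stage 1 rate analysis survives with no stated method.

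Neither reading gives an estimator.

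**3. Does the missing-data reason reach TLV?** Neither document assigns TLV an MMRM. Beyond pain and fatigue, protocol Section 11.4.5 plans one for the other PROs. Protocol Section 9.4.1 schedules Stage 1 MRI at screening and Months 1, 9 and 18, so there is no Month 24 scan to be missing. Kidney and liver volumes are read from the same MRI (note n to the study flow charts). For TKV, SAP 4.3.1.2 still fits the slope to all observed data at actual scan dates. Protocol Appendix O lets MRI wait until site visits resume, so actual dates matter for TLV too.

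**4. Dates.** Protocol amendment 07, which has >2 L/m, is dated 19 April 2021. The DMC futility review was on 14 May 2021 (SAP 4.9.2). SAP version 2 is dated 22 June 2021.
- 14 May to 22 June: 17 + 22 = 39 days.
- 19 April to 22 June: 11 + 31 + 22 = 64 days.

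The SAP Version History still says that this SAP was approved before the futility analysis, which is not true of version 2.

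**5. Illustration only: what by-visit summaries could cost.** The documents give no TLV variances, so the TKV components in protocol Appendix J stand in: intercept 0.017647, covariance 0.000105, slope 0.000218, residual 0.000658. Assume 80 per arm, scans at 0, 1/12 and 0.75 years for everyone, and at 1.5 years for a fraction f.

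- Mixed model: each participant contributes X′V⁻¹X, where V = XGX′ + 0.000658·I and G holds the intercept and slope components. Sum over 80(1−f) participants with three scans and 80f with four, invert, and take the slope variance.
- From a by-visit table: Month 18 mean change divided by 1.5. Its variance is (0.000218 + 2 × 0.000658/1.5²)/(80f) = 0.000803/(80f).

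| f | Mixed-model SE | Month 18 change/1.5, SE | Variance ratio |
|---|---|---|---|
| 0.30 | 0.0040 | 0.0058 | 2.07 |
| 0.50 | 0.0036 | 0.0045 | 1.57 |
| 0.70 | 0.0032 | 0.0038 | 1.36 |

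SEs are in log10 units per year. The 80 cancels from the ratio but not from the SEs. The SEs therefore do not carry over to an htTLV subset of unknown size, and the ratio holds for TLV only if its variance components resemble those of TKV.

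**The case against.** **A reader might infer that the SAP abandons the TLV rate.** The documents do not establish that. The Table 1 sentence replaces an MMRM, which TLV is never assigned in either document. TLV has its own row there, and that row cancels only the combined-stage analysis. Coming straight after TLV in Section 4.5.2, the word for the remaining endpoints most naturally leaves TLV out. The planned-visit sentence in Section 5.4 names TKV as well, and TKV still gets a slope model, so it does not settle the matter. The general annualized-rate rule in Section 5.4 can be read as covering TLV. All of this stands, and it is why the point is a missing method and an inconsistency.

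**A reader might also infer that the threshold was chosen on seeing results.** Nothing supports that. Table 1 logs the change openly with a rationale. SAP 4.9.2 lists TKV, eGFR and safety data as what the DMC reviewed, not TLV, and limits unblinded results to a small sponsor group outside study conduct. The documents date the approval of version 2, not when the change was first proposed.

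**The precision figures are fair game too.** They use TKV variances and assumed Month 18 completeness, against an estimator the SAP never proposes.

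Finally, TLV is exploratory, lies outside the multiplicity graph, and belongs to a trial stopped for futility. That limits the importance of the point. It does not supply the missing method or make the Table 2 lead-in accurate.

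**Conclusion.** The point holds in a limited form. SAP version 2 retains a Stage 1 TLV growth rate without an estimator; Table 1 and Section 4.5.2 disagree on what is to be done; and the reason given for descriptive summaries does not apply to a slope model. Separately, the Table 2 lead-in is wrong for the TLV population, and the protocol's >2 L/m result is not planned. The change to >1 L/m is disclosed, came in a version dated after the futility review, and is not shown to be data-driven.

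No confirmatory conclusion, alpha allocation or sample size is affected. The loss cannot be sized from the documents. As an illustration under TKV variances, recovering a rate from the Month 18 summary would carry about 1.4 to 2.1 times the variance of the mixed-model slope when 70% down to 30% of participants have that scan. The case for change is that a retained endpoint should be estimable from its own plan, and that making it so is cheap.

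**What to change.** 1. In SAP 4.5.2, state that Stage 1 TLV is analyzed with the Section 4.3.1.2 mixed model fitted to log10(TLV) on observed data at actual MRI dates. Report the rate in each arm and each dose minus placebo, with 95% CIs, as descriptive results.
2. Amend the Table 1 row so that it excepts Stage 1 TLV and agrees with Section 4.5.2.
3. Report the protocol population (htTLV >2 L/m) beside the >1 L/m population, labelling the second as introduced in SAP version 2 after the futility review.
4. Correct the sentence introducing Table 2, and the Version History statement on approval before the futility analysis.

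The cost is a few lines of text and two runs of a model already programmed for TKV; the >2 L/m set is nested in the >1 L/m set. The downside is that the >2 L/m set may be small, with a wide interval. If it is too small to fit, list the individual values and say so.
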